#### 6.2.3 Other methods for minimising bias

The content of the conversation between the test persons and the examiner is kept to a minimum.

### 6.3 Unblinding Procedures (Code break)

There is no provision for the removal of the blinding of the statistician and the examiners.

The blinding of the examiners and the statistician is only permissible if an unforeseen incident would occur.

In the event of incidents (AEs) that occur during or shortly after study participation and may be attributable to the intervention, the principal investigator may, at his or her discretion, immediately waive the blinding of the study participant and the investigators present to ensure adequate treatment of the study participant.

In the case of incidents (AE) that occur longer than 24 hours, clarification by a doctor is mandatory and a doctor's certificate is required for the lifting of blindness. Data may then also be passed on to the attending physician with the consent of the study participant concerned. This approach is justified because no life-threatening incidents are to be expected due to the interventions used here.

## 7. CLINICAL INVESTIGATION POPULATION

### 7.1 Eligibility criteria

Subjects fulfilling all of the following inclusion criteria are eligible for the investigation:

- Signed Informed Consent by the participant

- Diagnosed gonarthrosis
- Planned implantation of a primary total knee endoprosthesis by the Regional Hospital Surselva AG

The presence of any one of the following exclusion criteria will lead to the exclusion of the subject:

- Decompensated hypertension in the affected area
- Acute inflammatory phlebitis in the affected area
- Patients with acute paroxysmal cold hemoglobinuria, or cryoglobulinemia
- significant vascular disorder in the affected area (e.g., due to previous frostbite, significant atherosclerosis, diabetes, or ischemic vascular disease)
- History of pulmonary embolism or risk factors for deep vein thrombosis or pulmonary embolism in the affected area
- Diseases such as active carcinomas or inflammation in the affected area, in which increased venous or lymphatic reflux is not desirable (as tumor cells and inflammatory parameters can be distributed throughout the body due to reflux)
- Severe or decompensated heart failure
- Raynaud's disease
- Hypersensitivity to cold
- Fear of cold/compression

The test subjects will be comprehensively informed about the process and possible risks before they are accepted to participate in the study. You will also receive the information in written form and have the opportunity to ask questions. The declaration of consent explains to them what their rights and obligations are when participating. In addition, they are informed that they may withdraw from participation at any time without giving reasons, without incurring any disadvantages as a result.

## 7.2 Recruitment and screening

### Recruitment

It is advertised in the consultation hours of the orthopaedists of the Regionalspital Surselva AG, [name] with the help of the created advertisement (see attachment). The exact texts have been prepared according to the checklist of the Cantonal Ethics Commission Zurich.

### Screening

At the first contact, the potential participants are informed about the course and risks of the study, as well as its conditions and the amount of compensation.

### Advertisement

The advertisement for the first contact can be found in the attachment.

## 7.3 Assignment to investigation groups

The group assignment is hidden with the help of a ticket in a sealed envelope, which is drawn under the supervision of the study director. This lot shows whether the subject is going through the Game Ready or Control intervention.

## 7.4 Criteria for withdrawal / discontinuation of subjects

If a participant withdraws from the study, the allocation lot is returned to the pot in a new envelope and a new participant is sought.

The already completed consent form is kept in the locked filing cabinet. In the event of a revocation of consent, the data and samples already collected must be included in the evaluation for scientific and security reasons. Only after the analysis are they anonymised (Art. 9 ClinO).

The conditions for the termination of the experiment were described in chap. 5.4.

There is no disadvantage for the participants in the event of a termination of the Study participation.

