Intervention:	
The Game Ready GR PRO 2.1 is a certified product that complies with European regulations, directives and standards.
 
The system can administer ice-free cold treatment and intermittent pneumatic compression treatment, providing healthcare professionals with options for different patients, procedures, injuries and rehabilitation stages.
 
The following intervention is performed according to the manufacturer's protocol for patients with primary total knee arthroplasty: 48 hours after the operation starts the Game Ready Intervention, if tolerable, with little compression (level 1 = 5-15 mmHg) and cooling at the coldest level tolerable by the participant (corresponds to program 2). The cooling should be perceived as "pleasant" by the participant. The intervention lasts one hour, of which 30 minutes are on and 30 minutes off cycles. The on cycle includes the duration of the intervention (cooling and compression), while the off cycles include the rest period. After 60 minutes, the device is removed. If compression is not tolerated, it can also be omitted (corresponds to program 1). The intervention is performed twice a day for the first four days after surgery. The coldest tolerable temperature level is determined anew with each treatment. The compression level can be increased depending on the participant. Medium compression may only be applied from the second day onwards (corresponds to programme 3).

Control intervention (if applicable):	
In order to obtain high-quality study results, the test subjects are exposed to only one experimental condition at a time. There are two groups. In order to maintain the quality of the study, a randomized controlled trial design will be chosen. The division into the groups is randomized. The data collected in this way is pooled by outcome or group.
 
The control group will receive ordinary physiotherapy treatment, without Game Ready application.

Number of subjects with rationale:	
n=28 (14 per group) G-Power analysis: effect size at 0.8

Duration of the investigation:	
May 2022 – December 2024

Investigation schedule:	
May 2022- subject –In (planned) June 2023- subject –Out (planned)

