#### **Randomization**

In order to produce a high-quality study, the subjects are each assigned to a group, which are later compared with each other.

The assignment is carried out randomly. Randomization is guaranteed by drawing a lot.

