## 6. CLINICAL INVESTIGATION DESIGN

### 6.1 General clinical investigation design and justification of design

Randomized, controlled trial

It is a clinical investigation concerning medical devices (MD), Category according to Art 6 ClinO-MD (A1), whereby a CE-certified medical device is tested in the intervention group.

The group size of the participants is n=28 people (per group n=14 people). The group assignment is randomized.

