## 11.2 Determination of Sample Size

A power analysis was performed using the G\*Power App (Düsseldorf, North Rhine-Westphalia, DEU), where a minimum number of 28 subjects was deemed necessary to ensure the statistical power (0.95) to detect a parameter difference at the 5% significance level. The figure below shows the G-Power calculation that was used to determine the sample size.

*Figure 4: Sample Size Calculation*

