## 11.4 Planned Analyses

### 11.4.1 Datasets to be analysed, analysis populations

Only complete data sets will be included in the study. Data that contains only part of the protocol is not included in the analysis. No new subjects are being sought to replace the missing data.

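### Section 7.4 puts a withdrawn patient's lot back in the pot for a new participant, which conflicts with 11.4.1 and can make a late replacement's arm predictable

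*Combined protocol and SAP*

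**What the plan says.** Section 3.6 of the protocol says of the method: "Randomization is guaranteed by drawing a lot". Section 7.3 adds the concealment step: "The group assignment is hidden with the help of a ticket in a sealed envelope, which is drawn under the supervision of the study director". Section 6.1 sets the size at 28, with 14 per group. No section says how many lots of each kind the pot holds.

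For a participant who withdraws, section 7.4 says that "the allocation lot is returned to the pot in a new envelope and a new participant is sought". Section 11.4.1, on the analysis populations, says: "No new subjects are being sought to replace the missing data".

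Four other provisions bear on the point:

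- **Follow-up:** it runs to six weeks after surgery (5.1).
- **Blinding:** participants are not blinded, and a separate examiner operates the device (6.2.2).
- **Eligibility:** it includes matters of judgement, such as being afraid of cold or compression (7.1). The study leader may also exclude someone over doubts that have no medical proof (8.5).
- **Analysis:** only participants who complete the whole protocol are analysed (11.3, 11.4.1, 11.5).

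**The concern.** There are two problems.

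First, 7.4 and 11.4.1 give opposite instructions on replacement. One could try to separate them by reading 7.4 as covering withdrawals and 11.4.1 as covering incomplete data. But a patient who withdraws before the six-week visit is both, and the plan does not say which rule then applies.

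Second, if 7.4 is followed, the lot that comes back may be of known type, because the withdrawn patient was not blinded and staff delivered or withheld the device. While many lots remain, this tells nobody much. When the pot is empty or nearly so, the returned lot is all or most of what is left, and a new envelope cannot hide it. Six weeks of follow-up means that withdrawals can occur after the last lot has been drawn. Someone who knows the next arm could then let that knowledge affect whom to approach or accept, and the eligibility rules leave room for it. Selection of this kind cannot be repaired in the analysis.

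Because the analysis keeps completers only, the withdrawn patient also drops out of the comparison while someone else takes the place.

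**Working it through.** The plan gives no figure for the predictability of allocation, so there is none to reproduce. The sample-size calculation is not involved.

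**Inputs.** From the plan: 14 per group (6.1), and return of the lot to the pot (7.4). Assumed: the pot starts with 14 + 14 lots; the observer counts draws and knows the withdrawn patient's arm; withdrawal rates and the delay before a lot returns, neither of which the plan gives.

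**1. One withdrawal while lots remain.** Suppose *m* lots have been drawn and a randomly chosen earlier participant withdraws. The pot then holds 29 − *m* lots. Averaging over the hypergeometric split of the *m* draws, the chance that the next draw has the withdrawn patient's arm is

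P(same arm) = [15 − *m*/2 − (28 − *m*)/54] / (29 − *m*).

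For *m* = 14 this is (15 − 7 − 0.259)/15 = 0.52. For *m* = 27 it is (15 − 13.5 − 0.019)/2 = 0.74.

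The next arm is certain only if the pot holds one kind of lot. With *k* lots in the pot, and withdrawal unrelated to arm,

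P(certain) = 2·C(14,*k*)/C(28,*k*), with 1.00 at *k* = 1.

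| Draws made | Lots in pot after the return | P(same arm) | P(next arm certain) |
|---|---|---|---|
| 14 | 15 | 0.52 | 0.000 |
| 20 | 9 | 0.54 | 0.001 |
| 24 | 5 | 0.59 | 0.04 |
| 26 | 3 | 0.65 | 0.22 |
| 27 | 2 | 0.74 | 0.48 |
| 28 | 1 | 1.00 | 1.00 |

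**2. All 28 drawn, *w* lots returned.** The same formula with *k* = *w* gives the chance that the first replacement's arm is certain:

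- *w* = 1: 1.00
- *w* = 2: 2·91/378 = 0.48
- *w* = 3: 2·364/3276 = 0.22
- *w* = 4: 2·1001/20475 = 0.10

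The last lot in the pot is certain in every case.

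**3. Net effect over a trial.** Without returns, a 14 + 14 pot has on average 2·14/(14 + 1) = 28/15 = 1.87 certain draws at its end. The best guess is right for 16.85 of 28 draws (60.2%).

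Now assume withdrawal of 15% in the device arm and 5% in the control arm, with replacements also able to withdraw. The expected number of replacements is 14·0.15/0.85 + 14·0.05/0.95 = 2.47 + 0.74 = 3.2. Certain draws per trial then depend on when lots return:

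| When lots come back | Certain draws per trial |
|---|---|
| No returns | 1.87 |
| Immediately (simulated) | about 2.1 |
| After three further draws (simulated) | about 2.5 |
| All after draw 28, one at a time, each refilled before the next | 1.87 + 3.21 = 5.1 |

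With the three-draw delay, about 62% of the 3.2 patients enrolled after draw 28 have a certain arm. That share applies only to late replacements. Over the whole trial the increase is 2.5 − 1.87, about 0.6 of a patient, and the best-guess rate rises from 60.2% to only about 61%.

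**4. Sensitivity.** At 20%/5% with the three-draw delay there are about 2.8 certain draws. Unequal withdrawal is not needed: at 10% in both arms there are about 3.1 late replacements (28·0.1/0.9), of whom about 60% have a certain arm. The chance that at least one late replacement has a known arm equals the chance of any withdrawal among the first 28. That is 1 − 0.85^14·0.95^14 = 0.95 at 15%/5%, and 1 − 0.95^28 = 0.76 at 5%/5%.

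**The case against.** The case on the other side is substantial, and most of it stands.

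- **A reader might infer that every returned lot discloses the replacement's arm, so that concealment fails outright.** The documents do not support this. The lot goes into a new sealed envelope among those not yet drawn, and until late in recruitment the next draw is close to even (0.52 after 14 draws, 0.54 after 20).
- **A fixed pot is predictable at its end anyway.** Under the three-draw delay the return rule adds only about 0.6 of a certain draw, and mostly shifts an existing weakness to a later point.
- **The pot's contents are an inference.** Section 6.1 gives group sizes only. A finite pot split 14/14 is the natural reading, but it is not stated.
- **If 11.4.1 governs, no replacement is enrolled** and the problem does not arise. That is a reason to settle the conflict, since 7.4 still stands as an instruction.
- **A reader might infer that lot reuse is what removes withdrawn patients, or that it conceals unequal withdrawal.** Their removal comes mainly from the completers-only rules in 11.3, 11.4.1 and 11.5. Section 7.4 itself requires data gathered before consent is revoked to be evaluated, and nothing prevents withdrawals from being reported by arm. Reuse only refills the place.
- **A reader might infer that the device arm will lose more patients.** The plan gives no evidence for this. A participant may stop the cold application alone (5.4), so poor tolerance need not mean withdrawal. The 15%/5% split is an illustration.
- **Nothing says that the study director counts draws or informs those who recruit.** But 7.3 has that person supervise the draws, and 8.5 gives the study leader discretion over exclusion, so the risk is not nil.

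**Conclusion.** The point holds in a limited form. Sections 7.4 and 11.4.1 conflict on whether a withdrawn patient is replaced. If 7.4 is followed exactly, and the pot holds 14 + 14 lots, the arm of a replacement drawn from an empty or nearly empty pot is predictable to anyone who keeps count. It is certain for the first replacement with probability 1.00, 0.48 or 0.22 when one, two or three lots have come back to an otherwise empty pot.

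Over a whole trial, certain draws rise from about 1.9 to between 2.1 and 5.1 under the assumed 15%/5% withdrawal. The timing of returns accounts for that range. This weakens concealment late in recruitment, in a trial with unblinded participants and discretionary eligibility items. It does not show that concealment fails throughout, or that any selection will in fact occur.

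**What to change.** Replace the sentence in 7.4 with wording such as: *A drawn lot is never reused; the withdrawn patient keeps the allocated arm and is reported by arm.* Then reconcile 7.4 with 11.4.1, so that one rule on replacement applies throughout.

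If the sponsor keeps replacements, each should take the next unused envelope from spares prepared in advance. The spares should belong to the same concealed, sequentially numbered list, made up by someone outside recruitment. Those who recruit should not know the balance of that list; otherwise its last envelopes can be deduced just as the last lots can now. Forbidding reuse does not by itself remove the roughly 1.9 certain draws at the end of a fixed 14 + 14 pot.

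The cost is a few sentences in 7.3, 7.4 and 11.4.1 and about an hour to prepare envelopes. The one downside is small: the final arms may not be exactly 14 v 14.

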## 8. CLINICAL INVESTIGATION INTERVENTION

### 8.1 Identity of the medical device under investigation

#### 8.1.1 Experimental Intervention (medical device)

The Game Ready GR PRO 2.1 builds on the groundbreaking Game Ready technology and is a multimodality recovery device for professional users. The system can deliver ice-free cold treatment and intermittent pneumatic compression treatment, providing healthcare professionals with flexible options for different patients, procedures, injuries and rehabilitation stages.

Proven principles such as PITCH (pause, ice, compression, elevation) can be taken to a new level with the state-of-the-art Game Ready GR PRO 2.1. Cumbersome procedures for cold treatment will be simplified with the compact, practical device. In addition, these can be monitored and controlled more consistently than conventional methods. The device is controlled via a touchscreen computer interface. The user can choose between different treatment modalities and easily change and monitor the settings for treatment duration, temperature and compression. The double-acting (cryotherapy and compression) and anatomically designed Game Ready cuffs can be used specifically for specific parts of the body.

This device is used for the treatment of post-traumatic, post-operative (medical and/or surgical) and acute injuries, as well as for the reduction of edema, swelling and pain when cold and compression are indicated. It works in a closed circle with the help of the cuff described above and is therefore hygienic and safe to use in the clinic. The device is already being used in several Swiss clinics and institutions.

Figure 3 - Game Ready GR PRO 2.1 (<https://gameready.com/gr-pro-cold-therapy-unit/>)

In addition to standard physiotherapy (see Chapter 8.1.2 for more information), the subjects in the intervention group will receive the following intervention (according to the manufacturer's protocol for patients with total knee endoprosthesis): 48 hours after the operation, the intervention starts, if tolerable, with little compression (level 1 = 5-15 mmHg) and cooling at the coldest level tolerable by the participant (corresponds to program 2). The cooling should be perceived as "pleasant" by the participant. The intervention lasts one hour, of which 30 minutes are on and 30 minutes off cycles. The on cycle includes the duration of the intervention (cooling and compression), while the off cycles include the rest period. After 60 minutes, the device is removed. If compression is not tolerated, it can also be omitted on the first postoperative day (corresponds to program 1). The intervention is performed twice a day for the first four days after surgery. The coldest tolerable temperature level is to be determined anew for each treatment. The compression level may be increased, although medium compression may only be applied from the second day onwards (corresponds to program 3).

#### Securing study participants

The Game Ready applications represent a commonly used cooling and compression intervention in the literature. Nevertheless, the test subjects can discontinue the treatment at any time if they feel unwell. During the cooling applications and measurements, at least one or two examiners will always be next to the test subject in order to discontinue the treatment in case of discomfort. Further precautions are described in chap. 3.7. Risk/Benefits Described.

### **8.1.2 Control Intervention (standard/routine/comparator)**

The test subjects receive standard physiotherapy, without Game Ready application. Standard physiotherapy after a total knee prosthesis includes the following interventions: The first physiotherapeutic treatment begins on the first postoperative day and consists of immediate loading of the operated leg (full weight bearing permitted according to the symptoms). Knee mobilisation with a passive movement machine and active knee mobilisation, instructed by the physiotherapist, are carried out. The treatment is carried out and documented by qualified and training physiotherapists at the Regional Hospital Surselva AG, [name]. The cooling applications with Game Ready do not conflict with standard therapy.

### **8.1.3 Labelling and Supply (re-supply)**

The Game Ready GR PRO 2.1 is a certified medical device that complies with European regulations, directives and standards (93/42/EEC, EN60601-1, EC 60601-1-2, CE 0086).

### **8.1.4 Storage Conditions**

The Game Ready must be stored inside a room. The appliance is therefore located all year round in a closed room at room temperature and low humidity.

## **8.2 Discontinuation or modifications of the intervention**

No further side effects are expected from participation in the study, as it is not an invasive method or drug intervention. As in chap. 8.5, the predefined inclusion and exclusion criteria as well as the health questionnaire are used to ensure safe participation. However, if reasons arise, the study participant reserves the right to withdraw from the study early. The test person reserves the right to exclude a participant from the study for the following reasons: safety aspects (feeling unwell, dissatisfaction of the participant), occurrence of one of the predefined exclusion criteria, at the request of the participant, revocation of consent (also possible without justification). Further information in this case can be found under chap. 9.2.5 and 7.4.

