#### Patient satisfaction [cm]

In order to evaluate the patient satisfaction of the intervention group (Game Ready), the test subjects are asked the question "How satisfied are you with the cooling intervention?" immediately after the intervention. With the help of the Visual Analog Scale, the test subjects rate their satisfaction with a number between 0 (not at all satisfied) and 10 (maximally satisfied). The measurement moments take place twice a day (each time after the cooling intervention) during the

hospital stay.

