## 5.4 Safety Outcomes

No further outcomes are included that serve safety. Discontinuation of the experiment is the responsibility of the examiners with regard to the subject's resilience. If this is estimated to be too low, the examiner can stop the experiment. If the subject does not feel well according to his or her own subjective assessment, he or she can discontinue the experiment and withdraw participation in the study. If the cold application is not justifiable for the test subject, he or she can discontinue the application. There are no disadvantages for him/her as a result. The current regulations of the Canton of Graubünden and those of the FOPH for protection against the coronavirus will be taken into account and implemented when conducting the study.

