### **11.5 Handling of missing data and drop-outs**

If a test subject does not complete the experiment, any data that has already been collected is retained, but is not further incorporated into the final data analysis.

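### Section 8.2 allows patients to be excluded from the study after allocation on broad grounds, including dissatisfaction; with no further measurement and a completers-only analysis, this puts the randomised comparison at risk, plausibly in favour of the device

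*Combined protocol and SAP*

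**What the plan says.** **Power to exclude.** Section 8.2 opens the list with "The test person reserves the right to exclude a participant from the study for the following reasons" and gives the reasons "safety aspects (feeling unwell, dissatisfaction of the participant), occurrence of one of the predefined exclusion criteria, at the request of the participant", followed by revoked consent. The role named is unclear, because the protocol elsewhere uses similar words for the participant; an examiner is probably meant. The act is exclusion from the study, and it is discretionary.

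**Criteria that are re-applied.** Section 7.1 lists ten exclusion criteria. Some can arise in any patient after knee surgery, for example "History of pulmonary embolism or risk factors for deep vein thrombosis or pulmonary embolism in the affected area". Others concern exposure to the device, for example "Fear of cold/compression" and hypersensitivity to cold.

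**A second route.** Section 5.4 says of the subject's resilience: "If this is estimated to be too low, the examiner can stop the experiment". The same section separately lets a participant discontinue only the cold application.

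**After exclusion.** Section 8.2 refers to 9.2.5 and 7.4. Section 9.2.5 covers incident reporting, and 8.4 says nothing further is needed. Neither schedules outcome measurements. The follow-up in 10.3.1 concerns ongoing adverse events only. Under 7.4, "the allocation lot is returned to the pot in a new envelope and a new participant is sought".

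**Analysis.** Sections 11.3 and 11.4.1 admit only subjects with the complete protocol. For non-completers, 11.5 says "any data that has already been collected is retained, but is not further incorporated into the final data analysis".

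**Satisfaction.** This is one of the ten primary outcomes. The question is "How satisfied are you with the cooling intervention", put to the device arm after each session.

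**The concern.** Exclusion criteria protect the comparison when they are applied before allocation. Applied afterwards, they let events that treatment may have caused decide who is analysed. The groups compared are then no longer those that randomisation produced.

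The opportunities for removal also differ between arms. Device patients have attended sessions that controls lack, are asked about satisfaction when controls are not, and are exposed to the stimulus that would reveal intolerance of cold or compression. Dissatisfaction is both a ground for exclusion and the low end of a listed primary outcome.

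If the patients who tolerate the device poorly leave and also do worse, the remaining device arm looks better than the allocated one, and intolerance, which belongs in the treatment effect, disappears. Because those who leave are not measured, changing the analysis set later cannot recover their outcomes.

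**Working it through.** **1. Does 8.2 act after allocation?** It does not say so directly. It stands under a heading on discontinuing or modifying the intervention and refers to 7.4, where a lot already drawn is returned. The reading is inferred but well supported. The timing of the draw relative to surgery is not stated.

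**2. Are the grounds tied to one arm?** By wording, none is. Feeling unwell, dissatisfaction, own request and revoked consent can occur in a control inpatient. Of the ten criteria in 7.1, two clearly depend on device exposure in practice (cold hypersensitivity, and fear of cold or compression). Cold-triggered conditions such as Raynaud's disease might also be revealed by it.

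**3. Are the occasions for removal equal?** No. The time table in 9.1 budgets 2 sessions × 4 days = 8 sessions of 60 minutes (480 minutes) in the device arm only, and 8.3 puts a staff member at each. How many fall before Day 4 depends on how the 48-hour start fits the four-day span. The argument needs only that controls have none. The satisfaction item is likewise absent from the control column of the test log.

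**4. Possible size.** The plan has no figure on this point to reproduce: it gives no drop-out or removal rate. From the documents come 14 per group (6.1) and the 5% level (11.4.2). The assumptions are: normal outcome with SD 1, no true effect, k = 1 to 3 device patients removed and not replaced (as 11.4.1 states), correlation r between the reason for removal and poor outcome, and a two-sided two-sample t-test at one time point.

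Expected bias = r × S_k / (14 − k), where S_k is the sum of the absolute expected values of the k lowest of 14 standard normal values (1.703, 1.208, 0.901):

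- k = 1: 1.703 / 13 = 0.131 × r
- k = 2: (1.703 + 1.208) / 12 = 2.911 / 12 = 0.243 × r
- k = 3: (1.703 + 1.208 + 0.901) / 11 = 3.812 / 11 = 0.347 × r

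A simulation (60,000 trials per row) agrees within Monte Carlo error and adds the chance of a significant result favouring the device (nominal 2.5%):

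| Removal from device arm only | Bias in SD, k = 1 / 2 / 3 | False positive favouring device |
|---|---|---|
| r = 0 | about 0 | about 2.5% |
| r = 0.3 | 0.042 / 0.073 / 0.105 | 3.2 / 3.7 / 4.4% |
| r = 0.5 | 0.065 / 0.118 / 0.175 | 3.6 / 5.1 / 6.4% |
| r = 1 | 0.132 / 0.241 / 0.349 | 5.7 / 10.3 / 15.7% |

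If the same number leaves both arms by the same mechanism, the bias is about 0 at every r. The error rate favouring the device then stays at 2.6 to 2.9% for r = 0.5; at r = 1 it reaches 3.5 to 4.9%, because trimming shrinks the within-group SD. Removal from the control arm only gives the mirror image, against the device.

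**5. Against the planning effect.** The synopsis gives 0.8 without its metric. If it is a standardised mean difference, the r = 0.5 range is 0.065 / 0.8 = 8% to 0.175 / 0.8 = 22% of it, and the worst case is 0.349 / 0.8 = 44%.

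**6. Do the rules agree with each other?** No. On revoked consent, 7.4 requires data already collected to be evaluated, while 11.5 leaves non-completers' data out. Section 7.4 seeks a new participant, while 11.4.1 says none is sought. Refilling the arm would restore the number but not the comparison, since replacements face the same exclusion rule.

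**The case against.** A reader might infer that most of these grounds can arise only in the device arm, so that removal must favour the device. The documents do not support that. Section 8.2 restricts no ground to an arm, and most 7.1 criteria can occur in either. The power is discretionary. Section 5.4 already allows the cold application alone to be stopped, and 8.1.1 adapts temperature and compression to tolerance, so intolerance need not mean leaving the study. Unblinded controls who leave because of pain or disappointment would push the result the other way.

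A reader might also take a low satisfaction score to trigger deletion. Section 8.2 lists dissatisfaction among safety aspects, with no threshold and no link to the scale. The 10 to 16% error rates cannot apply to satisfaction, because controls give no score to compare. For other outcomes those rates need removal to follow the outcome perfectly, which nothing suggests. The t-test is also simpler than the planned repeated-measures analysis.

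All of this stands, and it limits the claim on direction and size. It does not remove the defect. Nothing obliges staff to stop only the application rather than exclude. A patient who stops the application has arguably not completed the protocol under 11.3. Nor is this only the completers-only problem under another name: a wider analysis set has nothing to analyse once exclusion has ended measurement.

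**Conclusion.** The concern holds in limited form. Followed as written, 8.2 permits exclusion after allocation for reasons that treatment can influence, 8.4 and 9.2.5 provide no outcomes for those excluded, and 11.3, 11.4.1 and 11.5 leave them out. The randomised comparison is then not protected. Bias towards the device is plausible, because that arm has more occasions for removal, but it is not established.

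Under the assumptions stated (one to three of 14 removed, device arm only, no true effect), the size runs from about 0 to 0.35 SD, with 0.07 to 0.18 SD at a correlation of 0.5. It is about zero if removal is symmetric or unrelated to outcome. The removal rate and the correlation are assumptions that the documents neither support nor exclude. The change should be made before enrolment continues: it is cheap, and the lost measurements cannot be recovered.

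**What to change.** - **8.2 and 5.4:** separate stopping the device from leaving the study. State that the 7.1 criteria decide study entry only, and delete dissatisfaction as a reason for exclusion from the study. Name the role that takes the decision. The clinical rules on who may stop the device, and when, are left unchanged.
- **8.4 and 9.2.5:** patients who stop the device for any reason keep the Day-4 and week-6 measurements, unless they decline or withdraw consent.
- **11.3, 11.4.1 and 11.5:** analyse all randomised patients in their allocated group, and say how missing values are handled.
- **7.4 against section 11:** reconcile the passages on use of withdrawn patients' data and on replacement.
- **Reporting:** give removals from the study and device stops by arm, with reasons.

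The cost is rewording. The measurement visits are those already scheduled, and no staff or patients are added. One small downside is that the estimated effect may be somewhat smaller, because patients who do not tolerate the device are kept.
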